2.3. Hypotheses

2.3.1. Primary Hypotheses

The Test lens will be non-inferior to the Control 1 lens with respect to overall night driving performance. A non-inferiority margin of -0.25 will be used.

2.3.2. Secondary Hypotheses

1. The Test lens will be non-inferior to the Control 1 lens with respect to binocular low luminance high contrast visual acuity. A non-inferiority margin of 0.1 LogMAR will be used
2. The Test lens will be no different than the Control 1 with respect to low luminance low contrast threshold without glare.
3. The Test lens will be no different than Control 1 with respect to the percentage of roads signs correctly identified at night driving.
4. The Test lens will be no different to Control 1 with respect to the average distance to correctly identify a pre-determined road sign at night driving.
5. The Test lens will be no different than the Control 1 with respect to the percentage of hazards avoidance at night driving.
6. The Test lens will be no different than the Control 1 with respect to average pedestrian recognition distance at night driving.

3. TARGETED STUDY POPULATION

3.1. General Characteristics

Participants will consist of Open licensed drivers (aged 20-49 years) with more than one year of driving experience. Participants must be regular drivers with best-corrected monocular visual acuity of 20/20 (logMAR 0.00) or better in each eye. Participants must be regular soft contact lens wearers with refractive errors within the range of available study contact lenses supplied by JJVC with uncorrected astigmatism of no more than 1.00 DC.

3.2. Inclusion Criteria

Potential subjects must satisfy all of the following criteria to be enrolled in the study:

1. The subject must read, understand, and sign the STATEMENT OF INFORMED CONSENT and receive a fully executed copy of the form
2. Appear able and willing to adhere to the instructions set forth in this clinical protocol
3. Between 20 and 49 (inclusive) years of age at the time of screening
4. Presbyopic subjects must be habitual wearers of distance vision correction in both eyes.

5. The subject's vertex corrected spherical equivalent distance refraction must be in the range of -1.00 through -6.00 D (inclusive) in each eye
6. The subject's refractive cylinder must be ≤ 1.00 D in each eye.
7. Have spherocylindrical best corrected visual acuity of 20/20 or better in each eye
8. Be a current soft contact lens wearer in both eyes, defined as at least 5 days per week and 6 hours per day averaged over the past 30 days.
9. Hold a current Open driver's license
10. Be a regular driver (at least once per week)
11. Have at least one year of driving experience

3.3. Exclusion Criteria

Potential subjects who meet any of the following criteria will be excluded from participating in the study:

1. Currently pregnant or lactating
2. Any systemic disease (e.g., Sjögren's Syndrome), allergies, infectious disease (e.g., hepatitis, tuberculosis), contagious immunosuppressive diseases (e.g., HIV), autoimmune disease (e.g. rheumatoid arthritis), or other diseases, by self-report, which are known to interfere with contact lens wear and/or participation in the study
3. Use of systemic medications (e.g., chronic steroid use) that are known to interfere with contact lens wear, pupil size or accommodation
4. Any ocular allergies, infections or other ocular abnormalities that are known to interfere with contact lens wear and/or participation in the study. This may include, but not be limited to entropion, ectropion, extrusions, chalazia, recurrent styes, glaucoma, history of recurrent corneal erosions, aphakia, or corneal distortion
5. History of binocular vision abnormality or strabismus
6. Any current use of ocular medication
7. Any previous, or planned (during the course of the study) ocular surgery (e.g., radial keratotomy, PRK, LASIK, etc.)
8. Any grade 3 or greater slit lamp findings (e.g., edema, corneal neovascularization, corneal staining, tarsal abnormalities, conjunctival injection) on the FDA slit lamp biomicroscopy scale
9. Any previous history or signs of a contact lens-related corneal inflammatory event (e.g., past peripheral ulcer or round peripheral scar), or any other ocular abnormality that would contraindicate contact lens wear
10. Employee of clinical site (e.g., Investigator, Coordinator, Technician)

3.4. Enrollment Strategy

Study subjects will be recruited from the Institution/clinical site's subject database and/or utilizing Independent Ethics Committee (IEC) or Institutional Review Board (IRB) approved materials.

4. STUDY DESIGN AND RATIONALE

4.1. Description of Study Design

This is a one site, 4-visit, randomized crossover, bilateral dispensing clinical trial. Approximately 28 eligible subjects will be screened and enrolled to ensure a sample size of 24 after subjects who withdraw or are lost-to-follow-up.

The study begins with an Initial Visit (Visit 1). If a subject is found to meet all eligibility criteria, he/she will be scheduled for the next visit; otherwise, the subject will be deemed ineligible for this study.

At Visit 2, eligible subjects will be randomized and laboratory testing will be conducted on all test articles in a random order based on the randomization scheme. Subjective assessment of driving performance in both daytime and nighttime will be performed in a random order, based on the randomization scheme, in two different visits at Visit 3 and Visit 4. Unscheduled follow-up visits may occur during the study. The planned duration of lens wear is for the experimental procedures only (between 1-3 hours during visits 2-4). Participants will not have access to test articles at study closure.

4.2. Study Design Rationale

Crossover designs are a well-established study design in which subjects are exposed to multiple treatments during different time periods. This design was considered to reduce the influence of potential confounding factors such as age, gender, vision correction and driving performance. A washout period of 20 minutes or more between driving assessments is built in from the 15-minute lens settling time and the 5-minute acclimation inside the car. This will help reduce any potential carry-over effect. Since subjects will be performing the same task repeatedly driving track conditions are randomized for each test article in order to further reduce any potential bias.

4.3. Enrollment Target and Study Duration

- Approximately 28 subjects will be recruited for screening, with a target sample size of 24 subjects to complete the study
- Study enrollment is defined as the execution of informed consent
- The study will involve 4 visits and the study duration will be approximately 3 months, with an enrollment period of 1 month. Each subject will complete the study within 8 weeks, depending on weather and access to the driving track. Visits 1-3 will be separated by at least 24 hours, while visits 3-4 will be separated by at least 1 week.

4.4. Site Selection

[REDACTED] It is used extensively by Queensland University of Technology (QUT) researchers/experimenters in previous vision and driving studies. The center represents rural roads that include hills, bends, curves, intersections, lengthy straight sections and standard road signs and driving lane markings. [REDACTED]

5. TEST ARTICLE ALLOCATION AND MASKING

5.1. Test Article Allocation

Participants will wear all study lenses in a bilateral fashion. There will be three levels of randomization in this study: (1) Sequence of driving time (Day and Night) (2) Sequence of lens wear (Test, Control1 and Control2) and (3) Driving Route (A, B, C). Hazard and pedestrian locations will be randomized for each driving route.

Subjects will be first randomly assigned to one of two possible driving time sequences (Day/Night and Night/Day) using a 2x2 crossover design. Within each driving time (Day and Night) subjects will be randomly assigned to one of six possible lens wear sequences using a 3x3 Williams crossover design:

Table 1: 3x3 Williams design

Sequence	Period1	Period 2	Period 3
1	Test	Control 1	Control 2
2	Test	Control 2	Control 1
3	Control 1	Test	Control 2
4	Control 1	Control 2	Test
5	Control 2	Test	Control 1
6	Control 2	Control 1	Test

This design is balanced with respect to first carry-over effect as every treatment follows every other treatment the same number of times.

Within each time and lens type combination subjects will be randomized to a driving route (Route1, Route2 and Route3) to further reduce the potential for treatment bias. The randomization scheme will be generated using the PROC PLAN procedure from SAS Software Version 9.4 or higher (SAS Institute, Cary, NC). The study site must follow the randomization scheme provided and complete enrollment according to the randomization list and not pre-select or assign subjects.

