5.2. Primary Analysis Methods

Overall driving performance score will be analyzed using a linear mixed model; sequence of lens wear, period, lens type, first order carry-over, driving time (day or night) and the 2-way interactions: lens*time, sequence*time, period*time and carry*time will be included in the model as fixed effects. Age will be included as fixed covariate when appropriate. An appropriate covariance structure will be selected to model the correlation between measurements across periods within the same subject and driving time. Covariance structures that will be considered include:

- Compound Symmetry (CS)
- Heterogeneous Compound Symmetry (CSH)
- Unstructured (UN)
- Ante-dependence (ANTE(1))

For ANTE(1) structure, subject and driving time nested within subject will be included in the model as random effects. For the remaining structures only subject will be included as random effect. The covariance structure that returns the lowest Akaike Information Criteria Corrected (AICC) will be selected as the structure that best fit the data¹². Heterogeneous residuals covariance structures (R-side) across driving time will be considered when appropriate. The log-likelihood ratio test will be used to test for the homogeneity between the residual covariance structures. The Kenward and Roger method will be used for the denominator degree of freedom. Non-significant interactions at the 15% significance level will be excluded from the model. The interaction between lens type and driving time will be forced into the final model.

Comparisons between Test and Control 1 will be conducted overall across driving time and within each level of driving time. Results from the final selected model will be reported as least-square mean (LSM) differences with 95% confidence intervals.

The null and alternative hypotheses for non-inferiority of Test lens relative to Control 1 are as follows:

$$H_0: \mu_T - \mu_C \le -0.25 H_A: \mu_T - \mu_C > -0.25,$$

where μ_T and μ_C are the means of night driving performance score for Test and Control 1, respectively. Non-inferiority of the Test relative to Control 1 will be concluded if the lower limit of the 95% confidence interval of the LSM difference between Test and Control 1, at night driving time, is greater than - 0.25.

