APPENDIX A SAS SYNTAX CODE

Primary Endpoint:

Overall driving performance scores

PROC GLIMMIX DATA = ads plots=studentpanel; CLASS driveseq asper trta carry1a parcat5 subjid sexn; MODEL aval= age sexn driveseq|parcat5 asper|parcat5 trta|parcat5 carry1a|parcat5/ DDFM=KR2 S; RANDOM INTERCEPT / SUBJECT=subjid; **RANDOM INTERCEPT / SUBJECT = parcat5(subjid);** *only included if ANTE(1) is used; RANDOM asper / RESIDUAL SUBJECT=parcat5(subjid) TYPE=covariance matrix group=parcat5; **Remove GROUP = time from the statement above if the test for homogeneity is rejected at 5% significance level; COVTEST "Common Varaince" Homogeneity; **test for homogeneity used along with GROUP = time; LSMEANS trta*parcat5 /slicediff = parcat5 CL ; **Primary analysis; ESTIMATE "Night: Test vs Control1" trta -1 0 1 trta*parcat5 0 -1 0 0 0 1 / CL; **Other Analysis; ESTIMATE "Day: Test vs Controll" trta -1 0 1 trta*parcat5 -1 0 0 0 1 0, "Day: Test vs Control2" trta 0 -1 1 trta*parcat5 0 0 -1 0 1 0, "Night: Test vs Control2" trta 0 -1 1 trta*parcat5 0 0 0 -1 0 1 / ADJUST= bonferroni CL;

RUN;

Where ads: Analysis data set subjid: subject identification aval: overall driving performance score sexn: Gender driveseq: Lens wear sequence (6 levels) asper: Study Period (3 levels) trta: Study lens type (Test, Control1, Control2) parcat5: Driving time (day or night) carry1a: First order carryover effect covariance_matrix: CS, CSH, UN and ANTE(1). The covariance structure that returns the lowest AICC will be selected as the structure that best fit the data.

Secondary Endpoints:

Binocular distance visual acuity (LogMAR)

PROC GLIMMIX DATA = ads plots=studentpanel; CLASS TSEQPG2 aperiod trta carry1a subjid sexn ; MODEL aval= age sexn tseqpg2 aperiod trta carry1a / DDFM=KR2 ; RANDOM INTERCEPT / SUBJECT=subjid; *only included if ANTE(1) is used; RANDOM aperiod / RESIDUAL SUBJECT=subjid TYPE=covariance_matrix ; LSMEANS trta / CL; ESTIMATE "Test vs Control1" trta -1 0 1, *secondary analysis; "Test vs Control2" trta 0 -1 1 / CL; *other analysis; RUN; Where ads: Analysis dataset subjid: subject identification sexn: Gender tseqpg2: Lens wear sequence (6 levels) aperiod: Study Period (3 levels) trta: Study lens type (Test, Control1, Control2) carry1a: First order carryover effect covariance_matrix: CS, CSH, UN and ANTE(1). The covariance structure that returns the lowest AICC will be selected as the structure that best fit the data.

Low Luminance contrast threshold

PROC GLIMMIX DATA= ads;

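### Day/Night order is randomised but is in no driving model, and lens sequence is not stated to be balanced within it, so a learning difference between the two driving visits would widen the night confidence interval

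*Protocol*

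**What the plan says.** Protocol 5.1 and SAP 1.6 describe three levels of randomisation. The first is driving-time order: "Subjects will be first randomly assigned to one of two possible driving time sequences (Day/Night and Night/Day) using a 2x2 crossover design". The second is lens order: "Within each driving time (Day and Night) subjects will be randomly assigned to one of six possible lens wear sequences using a 3x3 Williams crossover". The third is route. Neither section says whether the six lens sequences are balanced or stratified within the two Day/Night orders. The list itself is not shown.

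The primary model in SAP 5.2 has these fixed effects: "sequence of lens wear, period, lens type, first order carry-over, driving time (day or night) and the 2-way interactions: lens*time, sequence*time, period*time and carry*time". Protocol 14.5 has a shorter list with no order or visit term either, and the driving models in Protocol 14.6 and SAP 6.2 are built the same way. In the SAP Appendix A code, the variable whose name might suggest driving order is the lens sequence: "driveseq: Lens wear sequence (6 levels) asper: Study Period (3 levels". Period therefore counts drives within a visit and does not separate runs 1-3 from runs 4-6.

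Protocol 4.2 recognises repetition as a hazard: "Since subjects will be performing the same task repeatedly driving track conditions are randomized for each test article". Step 3.2 of the visit procedures adds a familiarisation lap, and Visit 4 repeats the Visit 3 procedures.

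**The concern.** For a subject in the Night/Day order, the three night drives are the first assessed drives on the circuit. For a subject in the Day/Night order, they come after three day drives. If practice gains are concentrated in the first driving visit, the night period profile differs between the two groups. The period-by-time term fits one night profile, the average of the two, and each group's departure from it goes into the residual.

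The sole primary decision is whether the lower 95% limit of night Test minus Control 1 lies above -0.25, so a larger residual costs power. If, by chance, Test is driven first more often than Control 1 in one order group, the departure also moves the estimate. Balance of lens sequences over all subjects does not prevent this.

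**Working it through.** **Inputs**
- 24 completers, margin -0.25, variance 0.05, ICC 0.4/0.5/0.6 (Protocol 14.2, SAP 1.5).
- Lower limit of a 95% interval as the decision rule (SAP 5.2).
- Assumptions: 12 subjects per Day/Night order and 4 per lens sequence at night. Learning occurs in the first driving visit only, as a step of b and then b/2, so the difference between visits is 1.5b. The documents give no value, so 1.5b is varied over 0, 0.15, 0.30 and 0.60 Z.

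**The plan's own power table.** Within-subject variance = 0.05 x (1 - ICC)/ICC, which is 0.075, 0.05 and 0.033. In the two-sample form, SE² = 4 x variance/24 with 46 df. One-sided alpha 0.05 gives 71.2%, 85.4% and 95.2%, matching the stated 71/85/95. One-sided 0.025, which the 95% interval rule implies, gives 59.1%, 76.5% and 90.7%. That mismatch is a separate matter. The table is used here only to fix the within-subject variance at 0.05 (ICC 0.5).

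**Order as a main effect.** Adding 1.0 to every night score of one order group left the fitted contrast (-0.0532) and its SE (0.0711) unchanged. Only order-by-period matters.

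**Hand calculation for a difference of 0.30.**
1. The night-first profile is 0, 0.2, 0.3. Centred, it is -0.167, 0.033, 0.133. The other group is flat.
2. The common period term takes the average, so each subject keeps half: 0.083, 0.017 and 0.067 in absolute value.
3. Sum of squares per subject = 0.0069 + 0.0003 + 0.0044 = 0.0117. Over 24 subjects this is 0.28.
4. Residual df = 48 - 6 = 42 (two each for lens, period and carry-over). The added residual variance is 0.28/42 = 0.0067.
5. The width ratio is √(0.0567/0.05) = 1.06.

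The sum of squares scales with b². A difference of 0.15 adds 0.0017 (ratio 1.02) and 0.60 adds 0.0267 (ratio 1.24).

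**Simulation of the night block** (within-subject fit of lens, period and carry-over; variance 0.05; 5,000 runs per cell). Entries are mean 95% half-width, with power in brackets.

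| Assumed difference (Z) | SAP terms, not stratified | Order-by-period, not stratified | SAP terms, stratified | Both changes |
|---|---|---|---|---|
| 0 | 0.1446 (92%) | 0.1484 (91%) | 0.1450 (92%) | 0.1449 (93%) |
| 0.15 | 0.1467 (92%) | 0.1488 (90%) | 0.1472 (92%) | 0.1453 (92%) |
| 0.30 | 0.1538 (89%) | 0.1483 (90%) | 0.1542 (90%) | 0.1448 (93%) |
| 0.60 | 0.1774 (77%) | 0.1487 (92%) | 0.1794 (83%) | 0.1453 (92%) |

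Under the SAP terms the widening is 0.1467/0.1446 = 1.01, 0.1538/0.1446 = 1.06 and 0.1774/0.1446 = 1.23. Power is 92% here, against 85% in the plan's table, because the crossover is analysed directly and not through the two-sample form.

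**Estimate and error rate under the SAP terms, not stratified.** The mean estimate stays within 0.0012 of zero. The SD of the estimate is 0.073, 0.072, 0.078 and 0.094 for the four differences. At 0.30 the chance shift has SD √(0.0782² - 0.0726²) = 0.029. One-sided type I error is about 2.5-3.2%.

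**Stratifying alone.** It removes the chance shift but leaves the learning difference in the residual. At 0.60 the interval is then too wide, and one-sided type I error falls to 0.8%.

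**The case against.** A reader might infer three stronger claims, none of which the documents support.

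- *Lens sequence is not crossed with Day/Night order.* The text is silent on this. A single generated list could already be balanced in all 12 combinations.
- *Learning biases the night contrast.* It does not do so in expectation. An order main effect cancels, and an order-by-period difference adds chance variation that the interval largely reflects.
- *The non-inferiority claim becomes easier to make falsely.* Type I error stays close to nominal, and a wider interval works against the sponsor.

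The size is also open to challenge. A learning difference of 0.30 Z between visits exceeds the 0.25 margin, and even that costs only about 6% in width and 3 points of power. The familiarisation lap, randomised routes and randomised hazard and pedestrian locations should reduce or spread learning. Period-by-time already removes average learning separately for day and night. An unstructured or heterogeneous residual matrix may absorb part of the rest, which the check, with its compound-symmetry-type residual, does not show.

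All of this stands, and it limits the priority. The gap itself remains: a factor that the trial randomises and that sets the run number is neither modelled nor stated to be balanced against lens sequence.

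**Conclusion.** The point holds as a conditional loss of precision. Day/Night order is absent from every driving model, and balance of lens sequence within it is not stated. If learning differs between the two driving visits, the night 95% interval at within-subject variance 0.05 is about 1% wider for a difference of 0.15 Z, 6% for 0.30 and 23% for 0.60. If learning does not differ, nothing is lost. Power drops materially, from 92% to 77%, only at the top of that range.

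These figures rest on an assumed learning curve confined to the first driving visit, equal order groups, and an analysis of the night block alone. The priority is optional to moderate. The case for acting is the negligible cost, not a demonstrated harm.

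**What to change.** 1. **Protocol 5.1 and SAP 1.6.** Generate the PROC PLAN list so that the six lens sequences are balanced within each Day/Night order, separately for the night and the day sequences, and say so. This gives 2 x 6 = 12 cells. Two completers per cell is the target at 24. It cannot be guaranteed, because 28 is not a multiple of 12 and dropout is not controlled by cell, so ask for cells as near equal as enrolment and dropout allow.

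2. **SAP 5.2, the driving models of SAP 6.2, and Appendix A.** Add Day/Night order and order-by-period within driving time as fixed effects. Coding period as runs 1-6 within driving time is equivalent. An order main effect alone does not help. State that these terms stay in the model regardless of the 15% removal rule, as the SAP already does for lens-by-time. The existing night Test versus Control 1 contrast needs no change.

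**Cost.** One change to the randomisation program, one extra class variable, and no new data. With both changes the half-width without learning is 0.1449 against 0.1446, so this is a free improvement. If the list has already been issued and only the model terms can be added, the half-width without differential learning is 0.1484/0.1446 = 1.026 times as wide, about 2-3%. In return, the half-width stays near 0.148-0.149 whatever the learning difference. That makes the model terms alone a cheap improvement, not a free one.
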